### Cystic Fibrosis Questionnaire – Revised (CFQ-R) Domain Scores

The recall period for this instrument is within the past 2 weeks. The domain scores are calculated as follows, as per University of Miami’s scoring guidelines:

First, item scores are assigned as values between 1 and 4. Next, items #6, #10, #13, #15, #17, #18, #23, #28, #30, #32, #34, #35, and #43 are reverse scored, where the new score is (5 – old score). If an item response is missing, the median value of scores for other items within that domain (e.g., #1 - #5, #13, #19, #20 for physical domain, and #40 – #42, #44 – #46 for respiratory domain) will be imputed, if no more than half of the responses for that domain are

Sponsor: SPYRYX Biosciences

Protocol no: SPX-101-CF-201

---

missing. If more than half of the answers for a specific domain are missing, that domain score will be missing.

The respiratory domain score is calculated as (#40 + #41 + #42 + #44 + #45 + #46 – 6)/18 \* 100. The physical domain score is calculated as (#1 + #2 + #3 + #4 + #5 + #13 + #19 + #20 – 8)/24 \* 100.

#### Concomitant Hypertonic Saline

For Cohort 1, concomitant hypertonic saline use will be identified by a review of all concomitant medication terms by ATC, preferred name, and verbatim term. The Medical Monitor or designee will review all concomitant medications (while blinded to treatment information) prior to database lock, and identify which medications are inhaled hypertonic saline. This information will be recorded on a spreadsheet, finalized prior to database lock, and incorporated into analysis datasets for use in summaries and analyses.

For Cohort 2, concomitant hypertonic saline use will be identified prior to randomization by the investigator or designee and will be entered into the Interactive Voice/Web Response System.

## **9.0 Analysis Sets**

### **9.1 Intention-to-Treat Analysis Set**

The Intent-to-Treat (ITT) Analysis Set will include all enrolled (randomized) subjects. Subjects will be grouped according to their randomized study group assignment regardless of the actual treatment received. The ITT population will be the primary population for all efficacy analyses.

### **9.2 Per Protocol Analysis Set**

The Per-Protocol (PP) Analysis set will include all subjects in the ITT population who did not have important protocol violations. Important protocol violations are defined as those that may have a substantial impact on efficacy assessments. The criteria to be used for excluding subjects from the PP population will be determined before database lock and will be documented. The PP analysis may be performed for the primary and secondary efficacy endpoints, to provide supportive evidence for efficacy.

### **9.3 Safety Analysis Set**

The Safety Analysis Set will include all enrolled subjects who receive at least 1 dose of the study drug. This analysis set will be used for all safety analyses.

## **10.0 Interim Analyses**

There was no interim analysis in this study. At the end of the Cohort 1 part of the study, all data was locked prior to review by the Sponsor which enabled selection of the Cohort 2 dosing regimens.

An independent DSMB will periodically review the accrued safety data in an unblinded manner to monitor the safety of subjects. There will be 3 scheduled DSMB meetings at the

following time points: the approximate midpoint of Cohorts 1 and 2 (after approximately 19 subjects have been randomized or at the discretion of the DSMB) and at the completion of Cohort 1.

## 11.0 Data Review

### 11.1 Data Handling and Transfer

Data will be entered into the clinical database and exported as SAS® datasets. Subsequent datasets will be created using SAS and following standard Clinical Data Interchange Standards Consortium Standard Data Tabulation Model (CDISC SDTM, version 1.3, Implementation Guide version v3.1.3) conventions. Analysis datasets will be created using SAS and following CDISC Analysis Data Model (ADaM, version 2.1, Implementation Guide 1.0) standards.

Medical history and AEs will be coded using the Medical Dictionary for Regulatory Activities (MedDRA), version 20.0 at the time of the analysis to assign a system organ class (SOC) and preferred term (PT) to each event. Prior and concomitant medications will be coded using the World Health Organization Drug Dictionary WHODRUG 2017SEP01 DDE+HD B2 at the time of the analysis.

Additional details can be found in the PRA Data Management Plan and the Data Quality Plan for this study.

### 11.2 Data Screening

Beyond the data screening built into the PRA Data Management Plan, the PRA programming of analysis datasets, tables, figures, and listings (TFL) provides additional data screening. Presumed data issues will be output into SAS logs identified by the word “Problem” and extracted from the logs by a SAS macro and sent to Data Management.

The PRA statistician and the SPYRYX Biosciences signatory must approve database lock.

## 12.0 Statistical Methods

All statistical programming will use SAS® version 9.4 or higher.

All statistical analyses will be performed using a two-sided alpha = 0.05, unless otherwise specified.

For two sequential cohorts, each cohort will be analyzed separately based on its own baseline.

Unless otherwise specified, descriptive summaries will be tabulated by treatment groups and overall. Categorical data will be presented using counts and percentages, with the number of subjects in each category as the denominator for percentages. Percentages will be rounded to one decimal place except 100% will be displayed without any decimal places and percentages will not be displayed for zero counts.

All continuous data will be summarized using the number of observations (n), mean, standard deviation (SD), median, first quartile, third quartile, minimum, and maximum. Minimum and maximum will be rounded to the precision of the original value. Mean and median will be

Sponsor: SPYRYX Biosciences

Protocol no: SPX-101-CF-201

---

rounded to one decimal place greater than the precision of the original value. The SD will be rounded to two decimal places greater than the precision of the original value.

## 12.1 Subject Disposition

The number of subjects screened will be tabulated. In addition, the number and percentage of enrolled (randomized), and the number of subjects in each defined analysis set (ITT, PP, safety) will be summarized by treatment group and total for all enrolled subjects.

Subject disposition will be summarized by treatment group and overall using the ITT analysis set. The table will present the number and percentage of subjects who completed study. The number and percentage of subjects who discontinued from the study will be summarized by the reason for study discontinuation collected in the CRF.

Disposition data will be listed by subject using the ITT analysis set.

## 12.2 Demographic and Baseline Characteristics

Demographic and baseline characteristics, including age (years and categories of <30, ≥30-<40, ≥40, sex, ethnicity, race, baseline height [cm], weight [kg], BMI and smoking tobacco history will be summarized descriptively by treatment group and total using the ITT analysis set.

Cystic Fibrosis (CF) history, including CF diagnosis, time from diagnosis to first dose date in years, the number of CF related hospitalization within past year and the number of pulmonary exacerbations within the past year will be summarized by treatment group and total using the ITT analysis set. In addition, the number of subjects who were concomitantly taking inhaled hypertonic saline and inhaled antibiotics during the treatment period will be summarized as above (Cohort 2 only). A listing of Cystic Fibrosis history will also be presented by treatment group and total using the ITT analysis set.

Baseline Spirometry, including absolute FEV1, ppFEV1, absolute FVC and ppFVC, will be summarized and listed by treatment group and total and by timepoints using the ITT analysis set.

## 12.3 Important Protocol Deviations

Per PRA processes, protocol deviations (PDV) data will be entered into our Clinical Trials Management System (CTMS). The study team and the sponsor will conduct on-going reviews of the deviation data from CTMS and the resulting set of evaluable subjects throughout the study, finalizing the PDV criteria as seems appropriate. The evaluable subjects set must be finalized at the post-freeze data review meeting (or earlier), prior to database lock.

Important protocol deviations (IPD) are a subset of protocol deviations that might significantly affect the completeness, accuracy, and/or reliability of the study data or that might significantly affect a subject's rights, safety, or well-being. IPDs will be summarized by category. The sponsor and study team will review and categorize IPDs. A list of subjects with IPDs will be presented.

## 12.4 Treatment Exposure

The investigational PARI eFlow nebulizer with PARI eTrack will be used for the dose administration. The 'Adherence Report' will be generated by the eTrack controller in the PARItrack web portal by the vendor.

The variables from PARI's 'adherence report' are the following:

- Start date and time
- Day of this subject's therapy
- Status of each nebulization
- Device serial number

There will be no additional summary of drug exposure and drug compliance in this SAP. A data transfer from PARI to PRA is not intended. An "adherence report" in PDF-file format through the PARItrack web portal will be available for inclusion in the eTMF.

## 12.5 Prior and Concomitant Medications

Prior/concomitant medications will be coded by World Health Organization Drug Dictionary (as per Section 8) and will be summarized by Anatomic Therapeutic Classification (ATC) class and preferred name. The analysis will be performed using the ITT population.

The numbers and percentages of subjects using each medication will be displayed. Subjects taking more than one medication in the same ATC class or preferred name will be counted once per ATC and once per preferred name.

Prior and concomitant medications will be listed, including start and stop dates, dose, unit, frequency, route of administration, indication and reason for administration.

## 12.6 Efficacy Analyses

The primary analysis, secondary efficacy endpoints and exploratory efficacy endpoints will be performed on the ITT analysis set. The primary and secondary efficacy endpoints will be repeated on the PP analysis set, to provide supportive evidence for efficacy, only if there are substantial differences from ITT.

### 12.6.1 Primary Variable

#### Primary Efficacy Analysis

The primary efficacy endpoint is the change from baseline in ppFEV1 at visit 5 (week 4). The change from baseline in ppFEV1 at each visit (Weeks 1, 2, and 4) will be summarized and compared between each treatment group and placebo. No imputation of missing data will be done for this analysis.

The comparison between each treatment group and placebo will be evaluated by using an analysis of covariance (ANCOVA) model, which will include treatment as the factor, and the stratification factor as a covariate (i.e., baseline lung function categories [ppFEV1 40.0% to 55.0% or 55.1% to 80.0% for Cohort 1] and the concomitant use of hypertonic saline for Cohort 2). Also included in the ANCOVA model for Cohort 2 is baseline ppFEV1. Descriptive statistics will include the number of observations, unadjusted mean, standard deviation, median, first quartile, third quartile, minimum and maximum, and least squares mean. Treatment differences from placebo will be presented and estimated by least squares means from the analysis model along with 95% confidence intervals and associated 2-sided p-values, which are presented for descriptive purposes.

Sponsor: SPYRYX Biosciences

Protocol no: SPX-101-CF-201

---

As described in the power and sample size calculations in Section 6.1, Cohort 1 will be evaluated for success using a two-sided 0.15 significance level. Cohort 2 will be evaluated for success using a one-sided (upper) 0.10 significance level. For Cohort 2, both the one-sided p-value and the lower bound (i.e. one-sided 90% confidence interval) will be presented.

The assumption of homogeneity of variance will be evaluated using Levene's test, on an ANOVA model with treatment as a factor, since Levene's test cannot be performed with an additional covariate in the model (i.e., the ANCOVA model). The assumption of normality will be evaluated using the Shapiro-Wilk test, applied to the raw residuals from the ANCOVA model. Both will be tested at the 0.05 level of significance. If Levene's test has  $p > 0.05$  but the Shapiro-Wilk test is significant, the ANOVA model with treatment as a factor will be evaluated for the assumption of normality. If that model meets criteria, it will be used as the primary efficacy analysis. If either Levene's test is significant, or the Shapiro-Wilk test is significant for both the ANCOVA and ANOVA models, a non-parametric Kruskal-Wallis test (for Cohort 1) or Wilcoxon-Mann-Whitney test (for Cohort 2) will be used to compare ppFEV1 between treatment arms. Note that both the Kruskal-Wallis and Wilcoxon-Mann-Whitney tests do not allow for covariates, so baseline lung function category will be excluded from the analysis.

In Cohort 1 only, the primary efficacy analysis will also be repeated comparing the combined SPX-101 treatment groups with the placebo group.

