#### **13.6.4 Efficacy**

##### **13.6.4.1 Primary Efficacy Analysis**

The primary endpoint is the change from baseline in ppFEV1 at Week 4 (Day 29). The change from baseline in ppFEV1 at each visit (Weeks 1, 2, and 4) will be summarized and compared between each treatment group and placebo.

The primary analysis for the change from baseline in ppFEV1 at Week 4 will be based on an analysis of covariance (ANCOVA). For Cohort 1, the model will also include the stratification variable baseline lung function categories (ppFEV1 40.0% to 55.0% or 55.1% to 80.0%). For Cohort 2, the model will include the stratification variable of concomitant use of hypertonic saline.

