### 7.6 Predetermined Covariates and Prognostic Factors

In Cohort 1, baseline lung function ppFEV1 categories (percent predicted forced expiratory volume in 1 second between 40.0% and 55.0% vs between 55.1% and 80.0%) will be included as a covariate in the model of the analysis of covariance (ANCOVA).

In Cohort 2, the use (yes/no) of concomitant hypertonic saline and baseline ppFEV1 will be covariates in the ANCOVA model.

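### A significant Levene test alone replaces the Cohort 2 primary ANCOVA with an unadjusted Wilcoxon test that has no stated estimate or one-sided 90% bound

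*SAP*

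**What the plan says.** Protocol 13.6.4.1 makes an ANCOVA the primary analysis and gives no fallback: "For Cohort 2, the model will include the stratification variable of concomitant use of hypertonic saline". SAP 7.6 and 12.6.1 keep that model for Cohort 2 and add baseline ppFEV₁ as a second covariate.

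For the result, SAP 12.6.1 states: "Treatment differences from placebo will be presented and estimated by least squares means from the analysis model". On the decision it says "Cohort 2 will be evaluated for success using a one-sided (upper) 0.10 significance level", and on reporting, "For Cohort 2, both the one-sided p-value and the lower bound (i.e. one-sided 90% confidence interval) will be presented".

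The same section then sets pre-tests at the 0.05 level: Levene on a treatment-only ANOVA, and Shapiro-Wilk on the ANCOVA residuals. If only Shapiro-Wilk is significant, a one-way ANOVA is tried next. Otherwise: "If either Levene's test is significant, or the Shapiro-Wilk test is significant for both the ANCOVA and ANOVA models, a non-parametric Kruskal-Wallis test" applies to Cohort 1, and for Cohort 2 a "Wilcoxon-Mann-Whitney test (for Cohort 2) will be used to compare" ppFEV₁ between the arms. A closing note says these "tests do not allow for covariates, so baseline lung function category will be excluded from the analysis".

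**The concern.** The word *either* makes a significant Levene test sufficient, whatever the residuals look like. Four things follow for Cohort 2.

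1. The Wilcoxon branch has no least squares means, and no other estimate or bound is named for it. The required one-sided 90% lower bound is undefined exactly where the decision is made by another test.
2. Hypertonic saline use (the stratification factor) and baseline ppFEV₁ both disappear. The note mentions only the baseline lung function category, which is the Cohort 1 covariate.
3. Wilcoxon is not a remedy for unequal variances, and 2:1 allocation makes this worse.
4. The sentence speaks of ppFEV₁, not its change from baseline.

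The branch is plausible. The protocol gives variability of response as one reason for Cohort 2, and a drug that helps only some patients makes the active arm more variable. In that case the rule mainly costs power. If instead the placebo arm is more variable with the same mean change, the false-positive rate exceeds 10%.

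**Working it through.** **Step 1. What SAP 12.6.1 requires, by branch (Cohort 2).**

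| Item | ANCOVA | Wilcoxon |
|---|---|---|
| Treatment difference | LS mean difference | none named |
| One-sided p-value at 0.10 | yes | yes |
| One-sided 90% lower bound | from the model | none named |
| Covariates | saline use, baseline ppFEV₁ | none |
| Variable | change from baseline | ppFEV₁, change not stated |

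The MMRM and the multiple-imputation ANCOVA still give adjusted differences, but with 95% intervals and 2-sided p-values.

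**Step 2. The plan's power (SAP 6.1).** Inputs: 30 active, 15 placebo, common SD 7.58, one-sided 0.10.

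- SE = 7.58 × √(1/30 + 1/15) = 2.397.
- Normal approximation: Φ(6/2.397 − 1.282) = 88.9% and Φ(8/2.397 − 1.282) = 98.0%.
- Noncentral t with 43 df: 88.4% and 97.9%.

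The stated 88% to 97% is reproduced to within about 1 point.

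**Step 3. Simulation of the decision rule.** 20,000 trials per case (standard error about 0.2 to 0.35 point).

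- *From the SAP:* 30:15, SD 7.58, pre-tests at 0.05, success at one-sided 0.10.
- *Assumed:* normal errors; saline use 50% in each arm; baseline uniform on 50 to 80; correlation of baseline with change −0.4; Levene on squared residuals (the SAP names no variant); the SD multipliers and responder shares below.
- *ANCOVA:* change = b₀ + b₁·treatment + b₂·saline + b₃·baseline + e, with 45 − 4 = 41 df.
- *HC3 variance:* (X′X)⁻¹ X′ diag[eᵢ²/(1 − hᵢᵢ)²] X (X′X)⁻¹. Lower bound = b₁ − t(0.90; 41) × SE(HC3).
- *Responders:* each mix has mean effect 6 (0.6 × 10, 0.5 × 12, 0.4 × 15, 0.3 × 20). If a gain g in a share p adds to an SD of 7.58, the active SD is √(7.58² + p(1 − p)g²). For 40% gaining 15 this is √(57.5 + 54) = 10.6, or 1.4 times 7.58.

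| Case | Plan | HC3 ANCOVA if Levene significant | HC3 ANCOVA always |
|---|---|---|---|
| *Null, target 10%* | | | |
| Equal SDs | 9.8 | 9.8 | 9.0 |
| Placebo SD 1.25× | 11.5 | 11.1 | 9.3 |
| Placebo SD 1.5× | 12.4 | 11.3 | 9.4 |
| Placebo SD 2× | 13.4 | 10.5 | 9.6 |
| Active SD 1.25× | 8.7 | 8.8 | 9.0 |
| Active SD 1.5× | 7.6 | 8.2 | 8.8 |
| Active SD 2× | 7.2 | 8.3 | 8.9 |
| *Power, mean effect 6* | | | |
| Equal SDs | 91.1 | 91.3 | 90.4 |
| Placebo SD 1.5× | 75.1 | 76.2 | 73.5 |
| Active SD 1.5× | 77.1 | 79.5 | 81.2 |
| Active SD 2× | 60.6 | 67.2 | 69.3 |
| 60% gain 10 | 85.4 | 86.1 | 86.1 |
| 50% gain 12 | 82.2 | 83.4 | 84.2 |
| 40% gain 15 | 76.8 | 79.8 | 81.4 |
| 30% gain 20 (extreme) | 66.2 | 74.2 | 77.2 |

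**Step 4. Is Wilcoxon a correction?** Null rates with no baseline correlation, 10,000 trials per case:

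- Placebo SD 2×: plain ANCOVA 15.1%, Wilcoxon 13.6%.
- Active SD 2×: plain ANCOVA 6.3%, Wilcoxon 8.6%.

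Wilcoxon moves the rate towards 10%. It removes (15.1 − 13.6)/5.1 = 29% of the departure in the first case and (8.6 − 6.3)/3.7 = 62% in the second.

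**Step 5. How often it matters.** Share of trials decided by Wilcoxon, by any route: 6% (equal SDs), 27% and 65% (active SD 1.5×, 2×), 45% and 85% (placebo SD 1.5×, 2×), 26% (40% gain 15). The Wilcoxon decision and the ANCOVA 90% bound disagree in 0.5% of all trials (equal-SD null), 3.4% (40% gain 15), 8.3% (30% gain 20) and 12.6% (active SD 2×, effect 6).

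**Step 6. Robustness.** An absolute-residual Levene test, 40 completers at 27:13, or zero baseline correlation leave the pattern unchanged. Across these checks, the null rate with placebo SD 2× is 12.7 to 13.1% under the plan and 9.9 to 10.2% with the Levene-branch change. Power for 40% gain 15 is 73.5 to 77.3% against 76.3 to 80.8%.

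**The case against.** The fallback is pre-specified with triggers and levels, and Protocol 13.3 lets the SAP expand on the methods. That stands: this is a poor rule, not a post hoc one.

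The level concern is conditional. Under the plan's common SD, or if the drug affects no one, the rule holds its level, and no document gives arm-specific SDs. Moderate cases show small power gains: 0.7 point (60% gain 10), 1.2 (50% gain 12), 2.4 (active SD 1.5×), 3.0 (40% gain 15). Gains above 6 points need a doubled active SD or the extreme responder mix. All of this stands and limits the weight of the point.

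Success is tied to the significance level, so the ANCOVA bound could simply be shown beside the rank p-value. That would fill the table, but Step 5 shows that the two can conflict, and the SAP does not say which then governs.

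The ambiguity over ppFEV₁ is minor, because the subsection defines the endpoint as change from baseline. Reading it as the Week 4 value would cut Wilcoxon power at a 6-point shift from 87% to 76%, so one clarifying word is worthwhile.

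Levene is not the only route. With right-skewed, equal-variance errors, about 82% of trials reach Wilcoxon while Levene is significant in only about 5.5%. Removing the Levene trigger leaves the missing estimate and bound untouched there, so any retained rank fallback needs its own.

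**Conclusion.** The concern holds and should be fixed before lock. Three parts rest on the text alone: a significant Levene test is sufficient to replace the ANCOVA, the branch has no defined estimate or one-sided 90% bound, and the covariate note does not describe Cohort 2.

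The practical size rests on assumed variance ratios. False-positive rates are 1.5 to 3.4 points above 10% when the placebo SD is 1.25 to 2 times the active SD. When the active arm is the more variable, the plan gives up about 1 to 3 points of power in moderate cases and 6.6 to 8.0 points in strong ones, compared with keeping the ANCOVA with HC3 errors after a significant Levene test. Under equal-variance normal errors there is no material loss.

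**What to change.** For Cohort 2, before database lock:

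1. Remove the Levene trigger to Wilcoxon. When Levene is significant, keep the ANCOVA of Week 4 change in ppFEV₁ with treatment, saline use and baseline ppFEV₁. Take the one-sided p-value and one-sided 90% lower bound for the LS mean difference from HC3 (or pre-named HC2) standard errors with residual degrees of freedom.
2. If a rank fallback is kept for non-normal residuals, use a van Elteren test stratified by saline use, or a rank ANCOVA, on change from baseline. Name the shift estimate and the one-sided 90% bound that decides success, for example Hodges-Lehmann by inverting the same test.
3. Correct the note so that it names the Cohort 2 covariates.

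Using van Elteren as the fallback, and keeping ANCOVA where the plan now moves to one-way ANOVA, shifted no rate by more than 0.6 point.

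**Cost.** SAP wording only. Under equal-variance right skew (exponential errors) the Levene-branch change costs 1.3 points of power (92.1 against 93.4%), or 2.2 with absolute-residual Levene. The null rate under equal-variance skew is 10.7%, against 10.0 to 10.4% for the plan. With placebo SD 2×, power is 59.0 against 59.6%. The change does not cure strong skew combined with unequal variances: right skew with placebo SD 1.5× gives 19.1% (plan 20.7%), and left skew with active SD 1.5× gives 16.7% (plan 16.9%).

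A simpler acceptable option is HC3 ANCOVA whatever the diagnostics show, with rank tests as sensitivity analyses. It removes data-driven test selection. Against the plan it costs 0.7 point of power under equal-variance normal errors, 1.6 with placebo SD 1.5×, 4.1 with t₃ errors and 2.5 to 5.7 under equal-variance skew. Its null rate is 11.3% with equal-variance right skew and 13.8% with right skew and placebo SD 1.5×.

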## 6.1 Sample Size Considerations

In Cohort 1, the study was planned for a minimum of 39 subjects per cohort to be enrolled. The subjects will be randomized in a 1:1:1 ratio to one of the two treatment groups or placebo. The sample size of 39 subjects provided 70% power for the Analysis of Variance (ANOVA) to detect a difference range of 4.5% to 6% in the change from baseline in ppFEV1 and FEV1 between the 2 treatment groups versus placebo, with the two-sided alpha level of 0.15 assuming a common standard deviation of 7%. The attrition rate is expected to be minimal given the 4 week treatment duration.

In Cohort 2, a total of 45 subjects will be randomized in a 2:1 ratio to SPX-101 120 mg BID or placebo. The sample size of 45 subjects will provide 88% to 97% power to detect a difference range of 6% to 8% in the change from baseline in ppFEV1 between the treatment group versus placebo, with the 1-sided alpha level of 0.1 assuming a common standard deviation of 7.58%. The estimated treatment difference and standard deviation are based on the Cohort 1 results from the 120 mg SPX-101 dose group and placebo, among subjects with baseline ppFEV1 between 50.0% and 80.0%, since this reflects the subjects enrolled in Cohort 2.

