#### Analyses of ppFEV1 at Additional Timepoints

The above approach will be repeated for testing treatment differences from placebo in the other timepoints, with a two-sided significance level of 0.05:

- Change from baseline in ppFEV1 at visit 3 (week 1)
- Change from baseline in ppFEV1 at visit 4 (week 2).

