## 13.0 Pooled Analyses Across Cohorts

The analyses specified in Sections 12 will be performed separately for each cohort, where applicable. In addition, the following summaries and analyses may be performed on the pooled cohorts for exploratory purposes. If performed, summaries and analyses will be presented by dose level (60 mg SPX-101 Cohort 1, 120 mg SPX-101 Cohort 1 and 2, and pooled placebo) and overall.

- Summary of subject disposition
- Summary of subject demographics
- Summary of CF history
- An ANCOVA as described in Section 12.6.1, using baseline ppFEV1 use as a covariate.

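### The Cohort 1 fallback in SAP 12.6.1 is a three-arm omnibus test with no pairwise step, so it cannot answer the dose-versus-placebo question the section asks

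*SAP*

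**What the plan says.** SAP 12.6.1 (Primary Efficacy Analysis) puts the Cohort 1 question dose by dose: "The comparison between each treatment group and placebo will be evaluated by using an analysis of covariance (ANCOVA) model". The decision level is given in the same section: "Cohort 1 will be evaluated for success using a two-sided 0.15 significance level".

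The section then sets assumption checks at 0.05. If Levene's test is significant, or Shapiro-Wilk is significant for both the ANCOVA and the ANOVA residuals, "a non-parametric Kruskal-Wallis test (for Cohort 1) or Wilcoxon-Mann-Whitney test (for Cohort 2) will be used to compare" ppFEV1 between arms. Covariates are dropped. No pairwise test follows, and SAP 12.6.6 adds no multiplicity procedure that could supply one.

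The rule extends to Weeks 1 and 2: "The above approach will be repeated for testing treatment differences from placebo in the other timepoints", there at two-sided 0.05. SAP 12.6.2 asks for similar ANCOVA analyses of the other spirometry endpoints without saying whether the fallback comes with them. SAP 13.0 allows an optional exploratory analysis of the pooled cohorts at three dose levels: "An ANCOVA as described in Section 12.6.1".

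**The concern.** The Kruskal-Wallis null hypothesis is that placebo, 60 mg and 120 mg share one distribution. Rejection says only that some arm differs from some other. It has no direction, cannot be assigned to a dose, and can arise because the two doses differ from each other or because one is worse than placebo.

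The Cohort 2 fallback is a two-group test and does answer its question, so the mismatch is confined to three-arm comparisons. With nothing else specified, and success in Cohort 1 tied to a 0.15 level, a small omnibus p-value could be taken as support for both doses. A dose with no effect could then be credited with the effect of the other.

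**Working it through.** **Inputs.** From SAP 6.1: 39 subjects at 1:1:1 (13 per arm), "detect a difference range of 4.5% to 6% in the change from baseline", and "assuming a common standard deviation of 7" percent, at two-sided 0.15. Protocol 13.2 gives 46 randomized (46/3 ≈ 15 per arm). Protocol 7.3.2 gives 40 completers (40/3 ≈ 13 per arm).

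**1. The plan's own figure.** Treat the 70% power as an omnibus one-way ANOVA with means 0, 4.5 and 6. The grand mean is 3.5 and the squared deviations sum to 12.25 + 1 + 6.25 = 19.5. The noncentrality is 13 × 19.5 / 7² = 5.17. The critical value of F(2, 36) at 0.15 is 2.00, and power is 69.8%, which matches 70%. Pairwise two-sided t tests give 56.6% at 4.5 and 75.8% at 6, so neither gives 70%. The sample-size basis therefore has the same omnibus form, although the protocol synopsis words it as each treatment group versus placebo.

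**2. Kruskal-Wallis rejection with one dose null.** Let the null dose equal placebo and the other dose be shifted by d. The large-sample noncentrality is approximately (3/π) × n × (2/3)d² / 7², referred to a chi-square with 2 df (critical value 3.79 at 0.15). For n = 13 and d = 6 this is 0.955 × 13 × 24 / 49 = 6.08, and power is about 77%. Simulation with normal errors (20,000 trials per row) gives:

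| Per arm | Other dose | Formula | Kruskal-Wallis rejects (simulated) | Pairwise Wilcoxon, null dose vs placebo |
|---|---|---|---|---|
| 13 | +3.08 | 37% | 36% | 15–16% |
| 13 | +4.5 | 57% | 55–56% | 15–16% |
| 13 | +6 | 77–78% | 75–76% | 15% |
| 15 | +3.08 | 40% | 39% | 15% |
| 15 | +4.5 | 62% | 60% | 15% |
| 15 | +6 | 82% | 81% | 15% |

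The +3.08 rows use the smaller Cohort 1 estimate in protocol 7.3.2. With all arms equal, Kruskal-Wallis rejects in 15–16%. Its size is correct; it tests a different hypothesis. With 13 per arm and d of 4.5 to 6, 28–38% of all trials are omnibus-significant with the null dose's mean above placebo's, which is about half of the rejections.

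**3. Conditioning on the SAP's trigger** (2,500 trials per scenario, 13 and 15 per arm, d of 4.5 and 6; every departure below is an assumption, since the documents give none):

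| Errors | Fallback fires | Kruskal-Wallis rejects, given it fired |
|---|---|---|
| Normal, SD 7 in all arms | 8–10% | 55–82% |
| t with 3 df, or exponential, scaled to SD 7 | 48–98% | 76–96% |
| Normal, SDs 7/7/14 or 4/7/10 | 62–76% | 28–66% |

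Across these scenarios the pairwise Wilcoxon test of the null dose rejects in 13–18% given the trigger. The firing rate under normal errors shifts a little with the form of Levene's test and the arm sizes, so about 8–11% is a fair range.

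**4. What was reported for Cohort 1.** Protocol 7.3.2 gives 3.08 (SE 2.411), p = 0.21, and 5.19 (SE 2.606), p = 0.05. The ratios are 1.28 and 1.99; on about 36 df these give p = 0.210 and 0.054. The reported p-values are those of per-dose model contrasts, not of an omnibus rank test.

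**The case against.** The strongest reply is that the issue is largely past. SAP 4.1 states that Cohort 1 was analysed under Version 1, which is not among the documents, so its fallback cannot be seen. Cohort 1 is locked and unblinded, and its Week 4 result was reported per dose. All of that stands. A reader might infer that the fallback influenced the primary result or the choice of 120 mg for Cohort 2; the documents point the other way.

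Second, a reader might infer that an ineffective dose will be declared different most of the time whenever the other dose works. The SAP contains no such rule. In the scenarios above one dose does work, so the omnibus rejection is correct for its own null. The rates become per-dose errors only if someone reads the omnibus p-value that way. They also depend on the scenario: they are 36–39% for a 3-point effect and can fall to 28% under assumed unequal variances.

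Third, per-dose information is not wholly lost. The Cohort 1 MMRM gives least squares differences from placebo with confidence intervals at Week 4 and is not conditional on the assumption tests. This is true, but it is a normal-theory analysis offered when the normal-theory ANCOVA has just been set aside, and it is not the designated primary analysis.

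Fourth, the pooled ANCOVA is optional, and SAP 12.6.1 assigns fallbacks only to Cohorts 1 and 2. That limits the claim there to an undefined fallback.

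The omnibus basis of the 70% power does not answer the point. The analysis section and the reported results are both per dose.

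**Conclusion.** The concern holds as a gap in specification. The Cohort 1 fallback does not test the hypotheses that SAP 12.6.1 sets out, and the SAP offers no route from the omnibus p-value to a conclusion about either dose. If that p-value were used per dose, the error for a null dose would be about 55–81% under the plan's inputs and about 35–40% with a 3-point effect in the other dose. It would be higher under the assumed non-normal errors. A pairwise Wilcoxon test holds about 15%.

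The practical reach is narrow. It covers any Cohort 1 analysis other than the reported Week 4 primary result that triggered the fallback (Weeks 1 and 2, and secondary spirometry if the fallback carries over), and the pooled analysis if it is run and borrows the rule. Whether any such analysis was reported by Kruskal-Wallis cannot be told from these documents.

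**What to change.** In SAP 12.6.1, make the three-arm fallback two rank tests: 60 mg versus placebo and 120 mg versus placebo. Use Wilcoxon rank-sum, or van Elteren stratified by the randomization ppFEV1 category. Say explicitly that they act on change from baseline, at the level already stated for that analysis, and report a Hodges-Lehmann shift with its confidence interval for each dose. Keep Kruskal-Wallis at most as a descriptive overall test. State the same pairwise fallback in SAP 13.0 in case the three-level pooled ANCOVA is run. In the clinical study report, add the two pairwise results for any Cohort 1 analysis that was reported by Kruskal-Wallis.

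The cost is a few lines of text and standard procedure calls, with no new data. The downside is two fallback p-values in place of one, which matches the two unadjusted ANCOVA comparisons already planned.
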